6.2.2.4. Sensitivity analyses for overall survival

All sensitivity analyses will be performed for PD-L1 positive patients and for patients unselected for PD-L1 expression.

The following sensitivity analyses will be performed to explore the robustness of the primary analysis results for OS. These analyses are regarded as purely exploratory. The sensitivity analyses will repeat the primary analysis (p-value, HR and 95% CIs) described in Section 6.1.2.1 with the modifications below:

- PP analysis set;

- unstratified;
- using strata derived according to eCRF data instead of that entered in IRT.

Methods for evaluating the validity of model assumptions

The same methodology described in Section 6.2.2.3 for PFS will be used for OS.

Exploratory analyses to investigate the impact of potential prognostic or effect modifying (predictive) factors

The same methodology described in Section 6.2.2.3 for PFS will be used for OS.

6.2.2.5. Objective response and tumor shrinkage

Best overall response (BOR) will be assessed based on reported overall lesion responses at different evaluation time points from the date of randomization until the first documentation of PD, according to the following rules. Only tumor assessments performed on or before the start date of any further anti-cancer therapies will be considered in the assessment of BOR. Clinical deterioration will not be considered as documentation of disease progression.

- CR = at least two determinations of CR at least 4 weeks apart and before first documentation of PD.
- PR = at least two determinations of PR or better (PR followed by PR or PR followed by CR) at least 4 weeks apart and before first documentation of PD (and not qualifying for a CR).
- SD (applicable only to patients with measurable disease at baseline) = at least one SD assessment (or better) \geq 6 weeks after the date of randomization and before first documentation of PD (and not qualifying for CR or PR).
- Non-CR/non-PD (applicable only to patients with non-measurable disease at baseline) = at least one non-CR/non-PD assessment (or better) \geq 6 weeks after the date of randomization and before first documentation of PD (and not qualifying for CR or PR).
- PD = first documentation of PD \leq 12 weeks after the date of randomization (and not qualifying for CR, PR, SD or non-CR/non-PD).
- NE: all other cases.

An objective status of PR or SD cannot follow one of CR. SD can follow PR only in the rare case that tumor increases by less than 20% from the nadir, but enough that a previously documented 30% decrease from baseline no longer holds. If this occurs, the sequence PR-SD-PR is considered a confirmed PR. A sequence of PR – SD – SD – PD would be a best response of SD if the window for SD definition has been met.

Objective Response (OR) is defined as a BOR of complete response (CR) or partial response (PR) according to RECIST v1.1.

Patients who do not have a post-baseline radiographic tumor assessment due to early progression, who receive anti-tumor therapies other than the study treatments prior to reaching a CR or PR, or who die, progress, or drop out for any reason prior to reaching a CR or PR will be counted as non-responders in the assessment of OR. Each patient will have an objective response status (0: no OR; 1: OR). OR rate (ORR) is the proportion of patients with OR in the analysis set.

ORR by treatment arm will be calculated along with the 2-sided 95% CI using the Clopper-Pearson method (exact CI for a binomial proportion as computed by default by the FREQ procedure using the EXACT option).

In addition, the frequency (number and percentage) of patients with BOR of CR, PR, SD, non-CR/non-PD (applicable only to patients with non-measurable disease at baseline), PD and NE will be tabulated. Patients with BOR of NE will be summarized by reason for having NE status. The following reasons will be used:

- No baseline assessment
- No post-baseline assessments due to death
- No post-baseline assessments due to other reasons
- All post-baseline assessments have overall response NE
- New anti-cancer therapy started before first post-baseline assessment
- SD of insufficient duration (<6 weeks after the date of randomization without further evaluable tumor assessments)
- PD too late (>12 weeks after the date of randomization)

Special and rare cases where BOR is NE due to both SD of insufficient duration and late PD will be classified as 'SD too early' (i.e., SD of insufficient duration).

The association of study treatment and OR will be tested by the General Association Statistic of the [Cochran-Mantel-Haenszel test \(CMH\)](#) with the randomization strata taken into account. The null hypothesis of no association in any of the randomization strata is tested against the alternative, which specifies that there is an association between study treatment and tumor response at least in one randomization stratum. The CMH test will be performed at 1-sided alpha level of 0.025.

The stratified odds ratio in terms of OR will also be estimated along with its 95% CI to compare study treatments. The odds ratio is defined as the odds of OR with experimental treatment divided by the odds of OR with control treatment. The Breslow-Day test will be used to check the homogeneity of the odds ratio across the randomization strata. It tests the null hypothesis that odds ratios in all strata are equal against the alternative hypothesis that at least in one stratum the odds ratio is different.

In case the null hypothesis of homogeneity of odds ratios across strata is not rejected at the 2-sided alpha level of 0.05, the common odds ratio will be determined using the Mantel-

Haenszel estimate (by the FREQ procedure using CMH option in SAS); if the null hypothesis of homogeneity of odds ratio across all strata is rejected, the odds ratio per stratum will be calculated with the corresponding exact CI.

BICR vs Investigator Assessment:

Table 13 outlines the possible BOR outcomes by investigator and BICR.

Table 13. Possible BOR Outcomes for Investigator vs BICR

BOR		BICR Assessment					
		CR	PR	SD	Non-CR/ non-PD	PD	NE
Investigator Assessment	CR	n_{11}	n_{12}	n_{13}	n_{14}	n_{15}	n_{16}
	PR	n_{21}	n_{22}	n_{23}	n_{24}	n_{25}	n_{26}
	SD	n_{31}	n_{32}	n_{33}	n_{34}	n_{35}	n_{36}
	Non-CR/ non-PD	n_{41}	n_{42}	n_{43}	n_{44}	n_{45}	n_{46}
	PD	n_{51}	n_{52}	n_{53}	n_{54}	n_{55}	n_{56}
	NE	n_{61}	n_{62}	n_{63}	n_{64}	n_{65}	n_{66}

$\sum_{i=1}^6(n_{ii})$ is the number of agreements on BOR between BICR and Investigator

$\sum_{i,j=1}^6(n_{ij})$ for $i \neq j$ is the number of disagreements on BOR between BICR and Investigator

$N = \sum_{i,j=1}^6(n_{ij})$

The following measures of concordance will be calculated for each treatment arm:

- Concordance rate for BOR = $\sum_{i=1}^6(n_{ii}) / N$
- Concordance rate for response = $[\sum_{i,j=1}^2(n_{ij}) + \sum_{i,j=3}^6(n_{ij})] / N$

Concordance rates are calculated for each treatment arm and, for each metric, the difference in concordance between the experimental and control arms are used to evaluate potential bias. If the concordance is similar across the treatment arms then this suggests the absence of evaluation bias favoring a particular treatment arm.

Tumor Shrinkage from Baseline:

Tumor shrinkage will be summarized as the percent change from baseline in target lesions (sum of longest diameter for non-nodal lesion and short axis for nodal lesion) per time point. It will be derived as:

- $((\text{Sum of target lesions at week XX} - \text{sum of target lesions at baseline}) / \text{sum of target lesions at baseline}) \times 100$

The maximum reduction in target lesions from baseline will be derived across all the post-baseline assessments until documented disease progression, excluding assessments after start of subsequent anti-cancer therapy, as:

- Minimum of $((\text{sum of target lesions at week XX} - \text{sum of target lesions at baseline}) / \text{sum of target lesions at baseline}) \times 100$

A waterfall plot of maximum percent reduction in the sum of longest diameter for non-nodal lesions and short axis for nodal lesions from baseline will be created by treatment arm. These plots will display the best percentage change from baseline in the sum of the diameter of all target lesions for each patient with measurable disease at baseline and at least one post-baseline assessment.

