2.2. Study Design

This is a Phase 3, multinational, multicenter, randomized (1:1), open-label, parallel 2-arm study in which approximately 830 patients, including a minimum of 580 PD-L1 positive patients, are planned to be randomized to receive either avelumab in combination with axitinib or sunitinib monotherapy.

- Arm A: avelumab plus axitinib;
- Arm B: sunitinib.

Patients will be stratified according to ECOG PS (0 vs 1) and region (United States vs Canada/Western Europe vs the rest of the world).

Crossover between treatment arms will not be permitted.

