5.1.1. Hypotheses and sample size determination

The following statistical hypotheses will be tested to address the primary objectives:

$$H_{01}: HR_{PFS+} \geq 1 \text{ vs } H_{11}: HR_{PFS+} < 1$$

$$H_{02}: HR_{OS+} \geq 1 \text{ vs } H_{12}: HR_{OS+} < 1$$

where HR_{PFS+} and HR_{OS+} are the hazard ratios (Arm A vs. Arm B) of PFS and OS, respectively, in PD-L1 positive patients.

In addition the following statistical hypotheses will be tested to address the secondary objectives:

[figure not shown]
$$H_{03}: HR_{PFS} \geq 1 \text{ vs } H_{13}: HR_{PFS} < 1$$

$$H_{04}: HR_{OS} \geq 1 \text{ vs } H_{14}: HR_{OS} < 1$$

where HR_{PFS} and HR_{OS} are the hazard ratios (Arm A vs. Arm B) of PFS and OS, respectively, for patients unselected for PD-L1 expression.

Overall type I-error will be maintained at or below 1-sided 0.025 by allocating $\alpha=0.004$ (α_1) to the PFS comparison in PD-L1+ patients and by allocating $\alpha=0.021$ (α_2) to the OS comparison in PD-L1 positive patients. A gatekeeping procedure will be used to allow further testing of PFS and OS for patients unselected for PD-L1 expression as described in Figure 1. The significance levels for each test will also take into account the group sequential nature of the design.

Figure 1 Testing Strategy

Approximately 830 patients, including a minimum of 580 PD-L1 positive patients, will be randomized to the treatment arms using a 1:1 randomization, stratified by ECOG PS (0 vs 1) and region (United States vs Canada/Western Europe vs the rest of the world).

For the primary PFS comparison, 336 PFS events by BICR assessment for PD-L1 positive patients will be required to have at least 90% power to detect a hazard ratio of 0.65 using a 1-sided log-rank test at a significance level of 0.004, and a 2-look group sequential design with Lan-DeMets (O'Brien-Fleming) α -spending function to determine the efficacy boundary and a Gamma Family (-15) β -spending function to determine the non-binding futility boundary.

For the primary OS comparison, 368 OS events for PD-L1 positive patients will be required to have at least 90% power to detect a hazard ratio of 0.70 using a 1-sided log-rank test at a significance level of 0.021, and a 4-look group-sequential design with Lan-DeMets (O'Brien-Fleming) α -spending function to determine the efficacy boundary and a Gamma Family (-3) β -spending function to determine the non-binding futility boundary.

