The sample size for this study is determined based on the following:

1. the median PFS for patients receiving sunitinib is 11 months (Sutent Summary of Product Characteristics) and the median PFS for patients receiving avelumab in combination with axitinib is 16.9 months for PD-L1 positive patients and 15.7 months for patients unselected for PD-L1 expression; this, corresponds to a hazard ratio (HR) of 0.65 and 0.7, respectively under the exponential model assumption;
2. the median OS for patients receiving sunitinib is 26.4 months (Sutent Summary of Product Characteristics) and the median OS for patients receiving avelumab in combination with axitinib is 37.7 months for PDL1 positive patients and 35.2 months for patients unselected for PD-L1 expression; this corresponds to a HR of 0.7 and 0.75, respectively under the exponential model assumption;

3. PFS drop-out rate of approximately 15% and OS drop-out rate of approximately 5%;
4. 70% of the randomized patients are PD-L1 positive;
5. non-uniform patient accrual accomplished over a 21 month period.

The sample size of approximately 830 patients will also allow an assessment of PFS and OS in patients unselected for PD-L1 expression.

If H_{01} is rejected then PFS in patients unselected for PD-L1 expression can be tested and 490 PFS events by BICR assessment will be required to have at least 90% power to detect a HR of 0.70 using a 1-sided log rank test at a significance level of 0.004, and a 2-look group sequential design with Lan-DeMets (O'Brien-Fleming) α -spending function to determine the efficacy boundary.

If either H_{02} or H_{03} are rejected, then OS in patients unselected for PD-L1 expression can be tested at the sum of the significance levels associated with the significant H_{02} and H_{03} tests (see Figure 1). With 534 OS events, the power is 91% (if both H_{02} and H_{03} are rejected), 90% (if H_{02} is rejected and H_{03} is not rejected) or 74% (if H_{02} is not rejected and H_{03} is rejected) to detect a HR of 0.75 using a 1-sided log rank test at a significance level of 0.025, 0.021 or 0.004, respectively, and a 4-look group sequential design with Lan-DeMets (O'Brien-Fleming) α -spending function to determine the efficacy boundary.

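### The SAP specifies an overall odds ratio for objective response only if a 5% Breslow-Day pre-test does not reject; it should be reported in every case

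*SAP*

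**What the plan says.** SAP 6.2.2.5 plans three results for objective response: the response rate by arm with a Clopper-Pearson CI, a stratified Cochran-Mantel-Haenszel (CMH) test at 1-sided 0.025, and an odds ratio. The odds ratio is introduced without a condition: "The stratified odds ratio in terms of OR will also be estimated along with its 95% CI to compare study treatments". The same section then makes its form depend on a test: "The Breslow-Day test will be used to check the homogeneity of the odds ratio across the randomization strata". The first branch begins "In case the null hypothesis of homogeneity of odds ratios across strata is not rejected at the 2-sided alpha level of 0.05" and leads to the Mantel-Haenszel common odds ratio. The second reads "if the null hypothesis of homogeneity of odds ratio across all strata is rejected, the odds ratio per stratum will be calculated", with exact CIs. No overall odds ratio is named for the second branch.

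The strata come from two ECOG levels and three regions (SAP 2.2). Under SAP 6.2.2 the analysis is done by BICR and by investigator, each in PD-L1 positive and in unselected patients, so the pre-test is run four times. Protocol 9.3.2 plans only the response rate by arm with exact CIs; the odds ratio is an addition in the SAP.

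**The concern.** The measure of treatment effect is chosen by a test on the same data. If the true odds ratio is the same in all strata, the pre-test will still reject at about its nominal level, and the reader then gets six imprecise odds ratios where one overall estimate was announced. Because the rule is applied four times, the tables could show a common odds ratio for one population or assessor and six separate ones for another, with nothing but chance behind the difference. Comparing populations, or BICR with investigator, on the odds ratio scale would then be difficult.

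What is at stake is the presentation of a secondary endpoint: one summary estimate and its CI.

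**Working it through.** **Inputs from the documents.** Pre-test level 0.05, 2-sided (SAP 6.2.2.5). Strata: 2 x 3 = 6 (SAP 2.2). Size: "Approximately 830 patients, including a minimum of 580 PD-L1 positive patients, will be randomized to the treatment arms using a 1:1 randomization", and "70% of the randomized patients are PD-L1 positive" (both SAP 5.1.1). Four analyses (SAP 6.2.2).

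**Assumptions.** Control response rate 31%, the BICR figure for sunitinib in the Phase 3 trial against interferon (protocol 1.2.2.3). Experimental rate 55.6%, the Phase 1b figure that includes unconfirmed responses (protocol 1.2.3). The documents give neither the distribution of patients over strata nor the agreement between assessors, so both are varied below.

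**1. Stratum size.** 0.70 x 830 = 581, which matches the stated minimum of 580. The averages are 580/6 = 97 patients (48 per arm) and 830/6 = 138 (69 per arm).

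**2. Chance per analysis.** Breslow-Day has 6 - 1 = 5 degrees of freedom and, under a common odds ratio, should reject with probability 0.05. This was checked with 40,000 simulated trials per scenario: N = 580 and 830; common odds ratio 1.5, 2.79 and 3.5; and four stratum splits (equal; ECOG 62/38 with regions 29/29/42; 75/25 with 20/30/50; 85/15 with 10/30/60). The rejection rate was 0.050 to 0.055, with a simulation standard error of sqrt(0.05 x 0.95/40,000) = 0.001. The plan's nominal level is reproduced and hardly depends on the split.

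**3. At least one of four.** If the analyses were independent: 1 - 0.95^4 = 18.5% for all four, and 1 - 0.95^2 = 9.8% for the two BICR analyses. They are positively related, because the populations are nested and both assessors read the same patients. In 20,000 simulated trials (580 within 830, split 75/25 with 20/30/50), the investigator call copied the BICR call with probability a and was otherwise drawn independently at the same rate:

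| a | Any of two BICR analyses | Any of four |
|---|---|---|
| 0.7 | 8.4% | 13.4% |
| 0.8 | 7.7% | 12.3% |
| 0.9 | 8.0% | 11.3% |

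**4. Loss of precision.** Odds ratio = (0.556/0.444)/(0.31/0.69) = 2.79. With n per arm, SE(log OR) = sqrt[(1/0.556 + 1/0.444 + 1/0.31 + 1/0.69)/n] = sqrt(8.73/n). Wald 95% CIs:

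| Estimate | n per arm | 95% CI | Upper/lower |
|---|---|---|---|
| Overall, N = 580 | 290 | 1.98-3.92 | 2.0 |
| Average stratum, N = 580 | 48 | 1.21-6.43 | 5.3 |
| Overall, N = 830 | 415 | 2.10-3.70 | 1.8 |
| Average stratum, N = 830 | 69 | 1.39-5.60 | 4.0 |

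The exact stratum CIs that the SAP specifies would be wider.

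**5. Value of the pre-test.** With real heterogeneity (stratum log odds ratios alternating +/-0.3 around the mean, odds ratio 2.79, split 75/25 with 20/30/50), the test rejects in only 22% of trials at N = 580 and 30% at N = 830. At +/-0.5 it rejects in 56% and 74%. Non-rejection is weak evidence that a common odds ratio is adequate.

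**The case against.** The rule is fully pre-specified: test, level, both branches and CI type are fixed, and the analyst has no discretion. Giving stratum odds ratios when homogeneity is rejected is a recognised convention, and if heterogeneity is real the rule does what it was meant to do. SAP 6.4 also plans BICR odds ratios with CIs by ECOG level and by region, in groups larger than the six strata. All of this stands, although that forest plot does not commit to an overall odds ratio.

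Four stronger readings are tempting and are not supported.

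- **The size of the response effect could go missing.** It could not. The rates by arm with exact CIs carry no condition and are the only objective response estimates that the protocol plans.
- **A p-value could stand with no matching estimate.** The SAP words the CMH alternative as an association in one or more strata, and stratum odds ratios with CIs do accompany a test of that alternative.
- **The fallback rests on tiny strata.** The averages are 97 and 138 patients. Smaller strata are possible, but only under assumed distributions.
- **A trial conclusion is at risk.** Objective response lies outside H01 to H04, and no stopping or success rule uses it.

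The text also does not say that the overall estimate is withheld on rejection, and its opening sentence is unconditional. But the two branches are the only specification of how the estimate is produced, and either/or is their natural reading. On the softer reading the section is ambiguous, and the same wording change settles it.

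**Conclusion.** The point holds as a free improvement. As written, the overall odds ratio and its CI depend on a 5% pre-test and, under a truly common odds ratio, give way by chance to less precise stratum estimates about 5% of the time in each of four analyses. That figure follows from the level in the SAP and is stable over the assumed stratum splits. The 11-13% for at least one of four is softer: it rests on an assumed split, assumed response rates and an assumed agreement of 0.7 to 0.9, with 18.5% as the independence bound. The effect is confined to one SAP-added summary of a secondary endpoint.

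The SAP already follows the better practice elsewhere. In 6.2.2.3 a large departure from proportional hazards adds a restricted mean survival time analysis for PFS and does not remove the hazard ratio.

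**What to change.** In SAP 6.2.2.5, remove the condition. Suggested content: the Mantel-Haenszel common odds ratio with its 95% CI is reported for each population and each assessor whatever the Breslow-Day result; the Breslow-Day p-value and the odds ratio in each randomization stratum with exact CI are reported as supportive information, in addition to the common odds ratio and not instead of it.

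The cost is one or two sentences. Both calculations are already planned, so no new data or method is needed. The chance of having no overall odds ratio under true homogeneity falls from about 5% per analysis to zero, and if heterogeneity is real the stratum results are still shown.

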The timing agreement of event is defined as a window of + 7 days

The following measure of discordance will be calculated for each treatment arm:

- Total Event Discrepancy Rate: $(b+c) / N$
- Early Discrepancy Rate (EDR): $(a3+b) / (a+b)$
- Late Discrepancy Rate (LDR): $(a2+c) / (a2+a3+b+c)$
- Overall Discrepancy Rate: $(a2+a3+b+c) / N$

The EDR represents the positive predictive value of investigator assessment and quantifies the frequency with which the investigator declares PFS event earlier than BICR within each treatment arm as a proportion of the total number of investigator assessed events.

The LDR quantifies the frequency with which the investigator declares PFS event later than BICR as a proportion of the total number of discrepancies within the treatment arm.

Discordance metrics are calculated for each treatment arm and, for each metric, the difference in discordance between the experimental and control arms is used to evaluate potential bias. If the discordance is similar across the treatment arms then this suggests the absence of evaluation bias favoring a particular treatment arm. A negative differential discordance for EDR and/or a positive differential discordance for LDR may be indicative of investigator evaluation bias in favor of the experimental arm (Amit et al, 2011).

Exploratory analyses to investigate the impact of potential prognostic or effect modifying (predictive) factors

See subgroups as defined in Section 6.4.

Multivariable Cox regression analysis will be carried out to assess and adjust the treatment effect for relevant baseline factors of potential prognostic impact. A stepwise selection procedure will serve to identify explanatory variables of potential prognostic values additional to the randomization strata which will be included in all models during the selection procedure. The Cox's Proportional Hazard model is defined as:

$$h(t) = h(0;t) e^{Xb}$$

where $h(0;t)$ defines the baseline hazard function and X defines the vector of explanatory variables and b the unknown vector of regression parameters.

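### SAP 6.2.2.5 reads similar BICR-investigator concordance as absence of evaluation bias, but concordance has no direction, so opposite miscalling in the two arms passes unnoticed when total disagreement is similar

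*SAP*

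**What the plan says.** SAP 6.2.2.5 cross-tabulates best overall response by investigator (rows) and BICR (columns) in Table 13. It defines two agreement rates per arm. BOR concordance is the diagonal total over N. Response concordance is the number of patients whom both readers call CR/PR, plus the number whom both call something else, over N.

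The section then says that "for each metric, the difference in concordance between the experimental and control arms are used to evaluate potential bias", and concludes: "If the concordance is similar across the treatment arms then this suggests the absence of evaluation bias favoring a particular treatment arm". It gives no margin for similarity, no directional measure and no sign rule.

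For PFS, SAP 6.2.2.3 handles the same question differently. It adds the early and late discrepancy rates (EDR and LDR) and names the sign of each between-arm difference that "may be indicative of investigator evaluation bias in favor of the experimental arm".

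SAP 2.2 describes a "randomized (1:1), open-label, parallel 2-arm study". SAP 3.2.2 lists objective response by investigator as a secondary endpoint alongside response by BICR, and SAP 6.2.2 analyses the two separately.

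**The concern.** Bias that favours an arm has a direction: more responses called by the investigator than by BICR in that arm, or fewer in the other. A rate that counts only whether the readers agree has discarded that direction. Two arms can have the same agreement rate while their disagreements run in opposite directions.

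At stake is the credibility of investigator-assessed objective response, and of TTR and DR derived from it, in a trial where investigators know the treatment. The study report could carry a prespecified statement that evaluation bias appears absent while the same table shows it.

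**Working it through.** The documents give no numerical figure for this rule, so there is nothing to reproduce. The check is on the form of the metrics, followed by illustrations.

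**Inputs.** About 830 patients randomized 1:1 gives 415 per arm; at least 580 PD-L1 positive gives 290 per arm (SAP 5.1.1). The agreement formulas and Table 13 are from SAP 6.2.2.5. Disagreement rates and BICR response rates are assumptions.

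**1. Symmetry.** Swap the two readers, that is, transpose Table 13. The diagonal does not change, and neither do the counts of joint response and joint non-response. Both concordance rates are therefore identical before and after. On an arbitrary table with N = 875, BOR concordance is 0.1657 and response concordance 0.6274 both ways, while over-calls minus under-calls over N flips from +4.6% to -4.6%. This result needs no assumed rate.

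**2. Exact example.** Take 415 per arm and BICR ORR 40% in both arms (166 responders, 249 non-responders). The investigator over-calls 42 patients in Arm A and under-calls 42 in Arm B.
- Concordance: (415 - 42)/415 = 89.88% in each arm, difference 0.
- Investigator ORR: (166 + 42)/415 = 50.1% against (166 - 42)/415 = 29.9%, a difference of 20.2 points.
- Odds ratio: (208/207)/(124/291) = 2.36, against 1.00 by BICR.
- Undirected error of the same size (21 up and 21 down in an arm) also gives 89.88%.

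With 415 or 290 per arm, BICR ORR from 31% to 50%, and about 5% to 15% miscalled, the concordance difference stays 0. The spurious ORR difference runs from 9.7 to 30.3 points and the odds ratio from about 1.5 to 4.6.

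**3. With sampling variation.** Total disagreement is 10% in each arm: 8% up and 2% down in Arm A, 2% up and 8% down in Arm B. The inflation of the investigator ORR difference is (8 - 2) - (2 - 8) = 12 points. The standard error of the concordance difference is sqrt(2 x 0.10 x 0.90/415) = 2.08 points. A 5-point gap is then 2.40 standard errors, and about 98% of trials fall inside it (98.2% in 20,000 simulated trials; 95-96% at 290 per arm). A 5% test of the concordance difference rejects in about 5% of trials, the same as with no bias. The 5-point yardstick is mine, because the SAP gives none.

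**4. The PFS metrics on a like pattern.** Per arm: 415 patients and 200 agreed events. The investigator misses 42 BICR events in Arm A and declares 42 extra events in Arm B. Total discrepancy is 42/415 = 10.1% in both arms. EDR is 0/200 = 0% against 42/242 = 17.4%, and LDR is 42/42 = 100% against 0/42 = 0%. Both differences carry the sign that SAP 6.2.2.3 associates with bias towards the experimental arm.

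**5. Which directional measure.** Over-calls minus under-calls over N equals investigator ORR minus BICR ORR, but it is not a clean indicator of bias. Over-calls come only from BICR non-responders and under-calls only from BICR responders. With the same error rate e in both arms and BICR response rate p, the net rate is (1 - p)e - pe = (1 - 2p)e. As assumed rates, take two figures in the protocol: 55.6% for the combination (1.2.3) and 31% for sunitinib (1.2.2.3). The Arm A minus Arm B difference is (-0.112 - 0.380)e = -0.492e, that is -2.5, -4.9 or -7.4 points for e = 5%, 10% or 15%. A Wald test at 415 per arm would reject in 35%, 62% or 79% of trials with no bias at all.

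Rates conditional on the BICR result remove this: each equals e in both arms, so the differences are 0. In the example of step 2 they show the bias. Over-call is 42/249 = 16.9% against 0%, and under-call is 0% against 42/166 = 25.3%.

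**The case against.** **The masking is not general.** It needs similar total disagreement in the two arms. If over-calling in Arm A comes on top of ordinary disagreement (13% up and 5% down, against 5% and 5%), total disagreement is 18% against 10%, and a 5% test of the concordance difference rejects in 92% of trials at 415 per arm (80% at 290). With 10% and 5% against 5% and 5% it rejects in 59%. This stands. Even so, the difference shows only that the arms disagree by different amounts, not which arm gains. And similar total disagreement is the very condition under which the SAP draws its inference.

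**The wording is mild.** The SAP says that similarity suggests absence of bias and attaches no test or consequence. This stands too: a reader might infer that the plan certifies investigator ORR as unbiased, and the text does not go that far.

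**The direction is already in the outputs.** ORR is planned by both readers with exact CIs, and Table 13 shows every off-diagonal cell. A careful reader could find a 12-point discrepancy there. That limits the harm, but it leaves a prespecified interpretation that the trial's own tables could contradict.

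**The stakes are small.** The hypotheses in the testing strategy concern PFS by BICR and OS, and subgroup response analyses use BICR. A reader might infer that the primary result is exposed; it is not.

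**Conclusion.** The inference is wrong as written. Neither concordance rate carries direction, so similar concordance says nothing about whether disagreements favour an arm. That part follows from the formulas alone. The sizes rest on assumed rates: a 12-point inflation of the investigator ORR difference in the 10% disagreement example, and 9.7 to 30.3 points across the range examined, with no expected difference in concordance.

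The documents do not support the stronger reading that the comparison would miss investigator bias in general. Bias that raises total disagreement in one arm can appear as a concordance difference, though without its sign. The effect is confined to investigator-assessed response endpoints. PFS by BICR, OS and BICR-based response are unaffected. The SAP should be changed, but nothing confirmatory depends on it.

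**What to change.** In SAP 6.2.2.5, delete the sentence that infers absence of bias and keep the two concordance rates as descriptive. Add, by arm, from Table 13:
- over-call rate among BICR non-responders = (n13+n14+n15+n16+n23+n24+n25+n26) / (total of BICR columns 3 to 6);
- under-call rate among BICR responders = (n31+n32+n41+n42+n51+n52+n61+n62) / (total of BICR columns 1 and 2).

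Report the Arm A minus Arm B difference in each with a 95% CI. State that a higher over-call rate and/or a lower under-call rate in Arm A may indicate investigator bias in favour of Arm A, in parallel with EDR and LDR in SAP 6.2.2.3. Net discordance over N may be shown as the net effect on the ORR difference, but not as a stand-alone test of bias, because it moves with the true response rate (step 5 of the working).

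The cost is a few derived lines from a table already planned, with no new data. The conditional rates take BICR as the reference, which is why the wording should stay at "may indicate".
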